6.4.2 Permitted Concomitant Medications and Therapies

Investigators may prescribe concomitant medications or treatments deemed necessary to provide adequate supportive care except for those medications identified as "prohibited" (Section 6.4.3). Administration of concomitant medications must be reported in the appropriate section of the eCRF.

• Palliative radiotherapy during the trial will be allowed for local pain control provided that:

(i) in the opinion of the investigator, the patient does not have progressive disease (PD) AND (ii) no more than 10% of the patient's bone marrow is irradiated AND (iii) the radiation field does not encompass a target lesion.

- G-CSF and other hematopoietic growth factors may be used in the management of acute toxicity, such as febrile neutropenia, when clinically indicated or at the investigator's discretion. Patients are permitted to be taking chronic erythropoietin provided that no dose adjustment was made within two months before the first dose of IMP.
- Blood-cell transfusion is allowed if clinically indicated.
- Chronic steroid therapy is acceptable provided that the dose was stable for at least 2 weeks before the first administration of GEN1029 and remains stable thereafter. The cumulative dose of corticosteroid within two weeks before the first infusion should not have been ≥ 150 mg prednisone (or equivalent doses of corticosteroids). Short-term steroid treatment is permitted at the discretion of the investigator.
- Tumor lysis syndrome (TLS): For patients at risk of developing a TLS, prophylaxis according to standard local practice with (aggressive) hydration, allopurinol, and/or rasburicase is recommended.
- Bisphosphonates (e.g. pamidronate, zoledronic acid, etc.) and denosumab.
- Multivitamins, vitamin D and calcium.

6.4.3 Prohibited Concomitant Therapy

Patients must be instructed not to take any medications, including over-the-counter products, without first consulting with the investigator.

The following medications and substances are prohibited during the trial:

- Any other investigational therapy.
- No dietary supplements are allowed during the trial period (except for multivitamins, vitamin D, calcium and supplements in prevention of weight loss). The use of traditional medicines is not permitted.

If a patient receives any of these during the trial, the sponsor must be notified for evaluation of whether the patient can continue treatment or not.

6.5 Trial Drug Information

6.5.1 Physical Description of Trial Drug

GEN1029 – 20 mg/mL formulated in **Sector** - is a clear colorless solution supplied as a concentrate for solution for infusion to be diluted (at site) in 0.9% NaCl (saline).

6.5.2 Packaging

IMP will be provided in a 10R/I tubular colorless glass vial containing 7 mL or 10 mL of GEN1029 (140 mg/vial or 200 mg/vial, respectively).

6.5.3 Labeling

IMP labels will contain information to meet the applicable regulatory requirements.

6.5.4 Preparation, Handling, and Storage

Each dose of IMP must be prepared by the site pharmacy using aseptic techniques.

All IMP must be stored at controlled temperatures ranging from 35.6 °F to 46.4 °F (2 °C to 8 °C).

Refer to the pharmacy manual or trial site investigational product manual for additional guidance on trial drug preparation, handling, and storage.

6.5.5 Drug Accountability

The investigator or designee must maintain an accurate record of the shipment and dispensing of IMP in a drug accountability log. Drug accountability will be noted by the field monitor during site visits and at the completion of the trial.

At trial close-out, and as appropriate during the course of the trial, the investigator will destroy all used and unused IMP, packaging, drug labels, and a copy of the completed drug accountability log to the monitor or to the address provided in the investigator folder at each site (unless otherwise agreed with sponsor).

6.6 Technical Complaint Handling

A technical complaint is defined as any suspicion of a product defect related to manufacturing, labeling, or packaging, i.e. any dissatisfaction relative to the identity, quality, durability, or reliability of a product, including its labeling or package integrity. A technical complaint may have an impact on the safety and efficacy of the product. Timely, accurate, and complete reporting and analysis of technical complaint information from trials are crucial for the protection of patients, investigators, and the sponsor, and are mandated by regulatory agencies worldwide. The sponsor has established procedures in conformity with regulatory requirements worldwide to ensure appropriate reporting of technical complaint information; all trials conducted by the sponsor or its affiliates will be conducted in accordance with those procedures.

6.6.1 Procedures

All initial technical complaints must be reported to the sponsor by the trial-site personnel within 24 hours after being made aware of the event.

If the defect is combined with a serious adverse event, the trial-site personnel must report the technical complaint to the sponsor according to the serious adverse event reporting timelines (Section 10.4.4). A sample of the suspected product should be maintained for further investigation if requested by the sponsor.

6.6.2 Contacting Sponsor Regarding Product Quality

The names (and corresponding telephone numbers) of the individuals who should be contacted regarding technical complaint issues are listed on the contact information page(s), which will be provided as a separate document.

7.1 Dose-limiting Toxicity

For the purpose of dose escalation, SAEs, non-serious (NS) \geq grade 3 AEs and clinically significant abnormal lab values will be collected and assessed by the DMC for DLTs (in each cohort during the first two cycles; i.e. DLT period of 28 days). National Cancer Institute (NCI) Common Terminology Criteria for Adverse Events (CTCAE) v.4.03 will be used to grade the intensity of adverse events.

DLT criteria are defined below:

Hematological

- Grade 4 neutropenia (i.e., ANC $< 0.5 \times 10^9$ cells/L) for minimal duration of seven days.
- Grade 3 and 4 febrile neutropenia (i.e., $ANC < 1.0 \times 10^9$ cells/L with a single temperature of > 38.3°C or a sustained temperature of ≥ 38°C for more than one hour).
- Grade 4 thrombocytopenia ($\leq 25.0 \times 10^9$ platelets/L) for minimal duration of seven days.
- \geq Grade 3 thrombocytopenia associated with bleeding.
- Grade 4 anemia.

Note: Any grade 4 hematological AE should be checked 2x/ week for up to 4 weeks until a repeated value below grade 2 is reported.

Non-hematological

- Grade 4 infusion-related reactions.
- Grade 4 anaphylaxis.
- Grade 3 infusion-related reactions that do not resolve to \leq grade 1 within 24 hours.
- At least possibly related grade 4 AST, ALT or bilirubin elevations.
- At least possibly related grade 3 AST, ALT or bilirubin elevations that do not resolve to \leq grade 1 within 7 days.
- At least possibly related AST, ALT or bilirubin elevations by more than one grade from baseline (e.g. grade 0→grade 2 as defined in the NCI-CTCAE Version 4.03) that do not resolve to ≤ grade 1 within 7 days.
- At least possibly related \geq grade 2 AST or ALT elevations with concomitant bilirubin >2.0×ULN with no signs of cholestasis, i.e. a Hy's law case.
- Re-occurring of at least possibly related AST, ALT or bilirubin elevations ≥ grade 3, observed in cycle 1 and again in cycle 2 independent of resolution.
- At least possibly related ≥ grade 3 amylase and/or lipase elevations with significant clinical symptoms that do not resolve to ≤ grade 1 or baseline within 7 days.
- Grade \geq 3 diarrhea that does not respond to optimal antidiarrheal treatment within 2 days
- Grade \geq 3 vomiting that does not respond to optimal antiemetic treatment within 2 days
- Grade 3 nausea that does not respond to optimal antiemetic treatment within 7 days

- Any ≥ grade 3 at least possibly related non-hematological AE, which occurs during the first two cycles *excluding*:
 - \circ Non-hematological laboratory abnormalities that have no clinical consequences and resolve to \leq grade 1 or baseline within 7 days (this also includes electrolyte abnormalities that respond to medical intervention).
 - Grade 3 fatigue persisting for less than 72 hours (optimal medical management must be applied).

Dose-escalation part of the trial:

- Patients experiencing a DLT (an AE fulfilling the DLT criteria within the DLT period of 28 days) must discontinue trial drug immediately.
- Meetings with the DMC will follow after completion of each cohort. Safety data for the specific cohort as well as cumulative safety data for all cohorts (SAEs, NS AEs, laboratory data and DLTs where applicable) will be evaluated.

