7.2.2.2 Infusion-Related Reactions

- Pre-medication to prevent infusion-related reactions may be administered at the investigator's discretion according to local guidelines (e.g., antihistamine, acetaminophen/paracetamol and corticosteroids). The use of paracetamol (acetaminophen) as pre-medication should be considered to be omitted to prevent transaminase elevations, and used with caution during all treatment cycles.
- Grade 1: If an infusion-related reaction grade 1 occurs, the infusion does not need to be interrupted and can be continued at the investigator's discretion at half the infusion rate under close medical supervision.
- Grade 2-3: If an infusion-related reaction grade 2 or 3 occurs, the infusion should be interrupted and appropriate medical management instituted. The infusion may be re-started at the investigator's discretion at half the infusion rate under close medical supervision if symptoms have resolved to ≤ grade 1 within an hour.
 - Patients who have experienced prior infusion related grade 2 or 3 reactions in the trial should be pre-medicated (antihistamine, acetaminophen and corticosteroids are recommended).
 - If the patient has a second Grade 3 infusion-related reaction despite pre-medication, the infusion should be stopped and the patient should be withdrawn from treatment.
- Grade 4: If anaphylaxis or grade 4 infusion-related reactions occur, administration of IMP should be discontinued immediately and permanently and appropriate medical therapy should be administered.

Please note:

- As a routine precaution, patients enrolled in this trial must be observed for 2 hours after each infusion, in an area with resuscitation equipment and emergency agents.
- At all times during GEN1029 infusion, immediate emergency treatment of an anaphylactic reaction according to institutional standards must be assured. In order to treat possible anaphylactic reactions, for instance, dexamethasone 10 mg and epinephrine in a 1:1000 dilution or equivalents should always be available along with equipment for assisted ventilation.
- All pre-medication must be reported on the concomitant medication page in the eCRF

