10.1.4 Definition of Infusion-Related Reactions

Infusion-related AEs are defined as any AEs occurring during infusion or where the onset of the event occurs within 24 hours after the end of infusion and is coded by Medical Dictionary for Regulatory Activities (MedDRA) preferred term as:

"Arthralgia", "Asthenia", "Bronchospasm", "Chills", "Cough", "Hyperhidrosis", "Dizziness", "Pyrexia", "Fatigue", "Flushing", "Headache", "Hypertension", "Hypotension", "Infusion related reaction", "Lethargy", "Malaise", "Myalgia", "Nausea", "Pruritus", "Tachycardia", "Tumor pain", or by MedDRA High Level term as "Exfoliative conditions" or "Dyspneas", "Dyspneas", "Breathing abnormalities" or by MedDRA High Level Group Term as "Allergic conditions".

Investigators should consider the clinical picture and isolated events, such as "Fatigue", occurring within 24 hours after the end of infusion, might be considered not to constitute an infusion-related reaction, if judged not to be infusion-related by the investigator.

For infusion-related reactions the causality of the event (Section 10.2.11) should be judged as "at least possibly related" by the investigator.

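### The last DLT bullet in protocol 7.1 makes the specific recovery windows for related non-hematological events inoperative, and neither document says which reading was applied to the primary endpoint.

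*Protocol*

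**What the plan says.** Protocol 7.1 lists the DLT criteria as bullets, each enough on its own. Several carry a qualifier:

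- Infusion reactions: "Grade 3 infusion-related reactions that do not resolve to" grade 1 or lower within 24 hours.
- Grade 3 or higher "diarrhea that does not respond to optimal antidiarrheal treatment within 2 days"; vomiting has the same 2-day rule, and grade 3 nausea a 7-day rule. None of these three requires relatedness.
- Related grade 3 or higher amylase/lipase elevations count if symptomatic and unresolved at 7 days.

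The last bullet takes in any event of at least "grade 3 at least possibly related non-hematological AE, which occurs during the first two cycles". It excludes two things: laboratory abnormalities without clinical consequences that resolve within 7 days, and "Grade 3 fatigue persisting for less than 72 hours (optimal medical management must be applied").

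Events "will be collected and assessed by the DMC for DLTs". In the 28-day DLT period, a patient with a DLT "must discontinue trial drug immediately". Section 10.1.4 says: "For infusion-related reactions the causality of the event (Section 10.2.11) should be judged as" at least possibly related. Section 7.2.2.2 lets a grade 2 or 3 infusion reaction be followed by restart "at half the infusion rate under close medical supervision if symptoms have resolved to" grade 1 or lower within an hour. Section 7.3 stops treatment at a second grade 3 reaction despite pre-medication, and Table 7-3 holds treatment for grade 3 diarrhea.

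SAP 17.1 takes the DLT definition from protocol 7.1 without comment, and SAP 5 (changes to protocol) does not mention it. The AE listing planned in SAP 17.3 carries a DLT flag.

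**The concern.** A window in a DLT criterion is there to keep a brief or treatable event from counting. If a later bullet in the same list counts the event anyway, the window has no effect. Two careful people could then classify the same patient differently: one reads the last bullet literally, the other reads it as covering only toxicities not already named.

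The DLT count is the primary endpoint and the sole numerical input to Table 4-3, so the choice of reading feeds directly into escalate, stay, de-escalate or terminate. The most exposed event is common here: 10.3.2 reports diarrhea in more than 40% of patients, mostly related, and as the most frequent SAE. It does not give the grade or how fast the events responded.

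**Working it through.** **Step 1. Each window against the last bullet.**

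| Event in cycles 1-2 | By its own bullet | By the last bullet |
|---|---|---|
| Grade 3 infusion reaction, settled within 24 h | Not a DLT | DLT (judged related under 10.1.4), except fatigue under 72 h |
| Related grade ≥3 diarrhea or vomiting, responds within 2 days | Not a DLT | DLT |
| Related grade 3 nausea, responds within 7 days | Not a DLT | DLT |
| Related grade ≥3 amylase/lipase, symptomatic, resolved within 7 days | Not a DLT | DLT |
| Same, asymptomatic, unresolved at 7 days | Not a DLT | DLT |
| Same, asymptomatic, resolved within 7 days | Not a DLT | Not a DLT (excluded) |
| Related grade 3 AST/ALT/bilirubin, no clinical consequences, resolved to grade ≤1 within 7 days, not recurring | Not a DLT | Not a DLT (excluded) |

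The diarrhea, vomiting and nausea windows still work for unrelated events. The liver windows largely agree with the last bullet because its laboratory exclusion uses the same 7 days. Section 2.3 attributes the Intensified Regimen DLTs to transaminases, so that finding is largely unaffected.

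**Step 2. Reproduce the decision rule.** Inputs: target 30% and borders 0.24 and 0.36 (4.3). With the usual BOIN multipliers 0.6 and 1.4 (assumed, not stated), φ = 0.30, φ1 = 0.18, φ2 = 0.42:

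- λ1 = ln(0.82/0.70) / ln[(0.30×0.82)/(0.18×0.70)] = 0.2365
- λ2 = ln(0.70/0.58) / ln[(0.42×0.70)/(0.30×0.58)] = 0.3585

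These round to the stated borders. The stated borders, with the termination rule of Table 4-4, reproduce every cell of Table 4-3.

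**Step 3. One reclassified patient.** 0/3 (0%) becomes 1/3 (33.3%), 1/6 (16.7%) becomes 2/6 (33.3%), and 2/9 (22.2%) becomes 3/9 (33.3%). Each goes from escalate to stay. In a cohort of 3 every added DLT changes the action: 0→1 escalate to stay, 1→2 stay to de-escalate, 2→3 de-escalate to terminate.

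**Step 4. How often this might matter (illustration only).** More than 40% with diarrhea is at least 11 of 27 (40.7%), if the base is the 27 patients in 2.3. The documents do not say how many had related grade ≥3 diarrhea in the first 28 days that responded within 2 days, with no other DLT. Assume 5%, 12.5% or 25% of a 40% share, so d = 2%, 5% or 10% of all patients. With other DLTs at rate p, the chance that the two readings give different Table 4-3 actions (trinomial) is:

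| Patients | p | d = 2% | d = 5% | d = 10% |
|---|---|---|---|---|
| 3 | any | 5.9% | 14.3% | 27.1% |
| 6 | 0% | 0.6% | 3.3% | 11.4% |
| 6 | 5% | 3.1% | 8.8% | 20.2% |
| 6 | 20% | 7.9% | 19.2% | 36.4% |
| 9 | 20% | 8.7% | 21.2% | 40.5% |

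For 3 patients the formula is 1 − (1 − d)³, because any discordant patient changes the action.

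**Step 5. A neighbouring inconsistency.** Section 4.3 treats a patient as evaluable if a DLT occurs before the 28-day period is complete. Protocol 11.1.4 and SAP 4.3.3 admit a patient who does not complete that period only for a DLT in cycle 1, that is, the first 14 days. Dropping one cycle 2 DLT turns 2/6 (33.3%, stay) into 1/5 (20.0%, escalate). It also turns 3/9 into 2/8 (25.0%), but both mean stay.

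**The case against.** - **The list is not contradictory.** A reader might infer that 7.1 contradicts itself. It does not: the bullets are alternatives, so taken literally a related grade 3 diarrhea counts. The gastrointestinal bullets keep a purpose for unrelated events, and other bullets overlap too. This stands. The defect is that windows are voided without saying so.
- **The care rules can coexist with the literal reading.** A reader might infer a general conflict with 7.2.2.2 and Table 7-3. Those rules cover all cycles and both trial parts, so hold and restart still operate after the DLT period. The conflict is confined to the first 28 days, where 7.1 and 7.3 require discontinuation.
- **The DMC decides, and its charter may state the reading.** So may the separate population-classification document named in SAP 4.3.3. Neither is available here, so the gap is shown only for the protocol and SAP. The AE listing would let a reader infer the reading from severity, causality, dates and DLT flag, but inference is weaker than a stated definition of the primary endpoint.
- **The probabilities rest on assumed event rates.** This stands. At 6 patients the range falls from 7.9-36.4% to 0.6-11.4% when there are no other DLTs. Only the Table 4-3 thresholds come from the documents.
- **Escalation is over.** SAP 3.3 and 4.5 say that the MTD has been identified. A protocol edit cannot change past decisions, but the SAP can still say how the reported count was formed.

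**Conclusion.** The point holds and should be fixed. As written, the last bullet makes the 24-hour window inoperative for grade 3 infusion reactions (apart from fatigue under 72 hours), and the 2-day and 7-day windows inoperative for related diarrhea, vomiting and nausea. It does so in part for amylase/lipase. The windows and the restart and hold rules suggest a residual clause was intended, but nothing gives the specific bullets precedence.

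The firm size is one patient: that is enough to change the action at 0/3, 1/6 or 2/9. Anything beyond that depends on event rates the documents do not give. A reader might infer that the declared MTD or a reported DLT count is wrong. The documents do not support that: the affected events are not counted anywhere, transaminase DLTs are largely unaffected, and the DMC may have applied one reading throughout. A recount could show how far the counts depend on the reading, but not the MTD that another reading would have produced, because later cohorts would have been dosed differently. Which clinical rule is right is for the sponsor and the DMC.

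**What to change.** (a) **Protocol 7.1.** State in the last bullet which reading holds. If the windows are meant to apply, exclude by name: grade 3 infusion-related reactions that resolve to grade 1 or lower within 24 hours (not anaphylaxis), diarrhea and vomiting that respond within 2 days, and nausea that responds within 7 days. Say which window governs nausea within 24 hours of an infusion, since 10.1.4 also lists nausea as an infusion-reaction term. Say whether grade 4 diarrhea or vomiting is exempt. Leave persistent grade 3 or higher amylase/lipase elevations under the last bullet unless the sponsor decides otherwise. A general exemption for types with their own criterion would be too wide: it would also remove related grade 3 anaphylaxis, whose own bullet covers grade 4 only.

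(b) **SAP 17.1.** Keep the DMC-assessed count as primary and state the reading the DMC applied. Flag in the planned AE listing the events whose DLT status differs between readings. Add a descriptive count per dose level to Table 14.03.01, labelled as not re-deriving the MTD.

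(c) **Separate correction.** In protocol 11.1.4 and SAP 4.3.3, admit a DLT at any time in the DLT period (days 1-28), to match 4.3.

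**Cost.** One clause in 7.1, one SAP sentence, one table row, one listing flag and a wording change to the analysis set. The documents show no field for response within 2 days. A working definition is needed, built from the dates of grade changes and the concomitant medications linked to AEs, for example grade 2 or lower within 2 days of the first antidiarrheal dose. The sensitivity count may look less favourable than the primary one.

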7.2 Dose Modification Guidance and Mitigation Plans for Specific Adverse Events

7.2.1 Dose modification Guidance

7.2.1.1 Handling of adverse events fulfilling the DLT criteria

Adverse events that fulfill the DLT criteria (after the DLT period has ended in the dose-escalation part of the trial or during the expansion part of the trial) should be handled as shown in Figure 7-1. *Please note that specific rules apply for elevated liver parameters (see Section 7.2.2.1).*

Figure 7-1: Handling of adverse events fulfilling the DLT criteria

BL=Baseline.

*Dose delay: Next dose of IMP can maximally be delayed 14 days unless approved otherwise by the sponsor medical monitor.

** If sponsor and investigator disagree, DMC should approve.

No delay for recovery from \geq G2 allowed.

Unless grade at BL was \geq G2 and AE has resolved to baseline grade.

Grade 4 AEs fulfilling DLT criteria will always lead to IMP discontinuation.

First occurrence of AE fulfilling DLT criteria grade 3:

- Investigator must contact sponsor for thorough discussion in order to decide whether the patient should be withdrawn from treatment or next dosing should be delayed.
- Administration of GEN1029 can be delayed for up to 14 days (i.e. one cycle). If the intensity resolves to \leq grade 1 or baseline within this period, re-treatment may be considered under the following conditions:
 - Sponsor and investigator (DMC may be consulted) will discuss any safety concerns in order to decide whether next dose of IMP should be administered at same dose level or one dose level lower (DL-1). In case investigator and sponsor disagree, the DMC must be consulted.

Second occurrence of an identical AE grade 3 after re-exposure to IMP:

- If re-treatment leads to an identical adverse event with same intensity, the next administration of GEN1029 can be delayed for up to 14 days. If the intensity of the AE resolves to ≤ grade 1 or baseline within this period, re-treatment may be considered under the following conditions:
 - Next dose of IMP should be administered at one dose level lower (DL-1 or DL-2) than the dose level causing the recurrence of the adverse event.

Third occurrence of an identical $AE \ge \text{grade 2}$ after re-exposure to IMP:

- If re-treatment at a lower dose leads to a third identical adverse event with intensity ≥ grade 2, the subject must permanently discontinue trial drug. No dose delay is allowed. However, if the adverse event is ≤ grade 1 or baseline, re-treatment may be considered under the following condition:
 - Next dose of IMP should be administered at same reduced dose level (DL-1 or DL-2).

Please note:

- Re-escalation of treatment dose is not allowed for patients that previously have been dose-reduced.
- IMP must be permanently discontinued if the patient experiences an adverse event fulfilling the DLT criteria (after the DLT period has ended for the dose-escalation part of the trial or during the expansion part of the trial) that fails to resolve to ≤ grade 1 or baseline within 14 days after the planned dosing date.
- IMP must be permanently discontinued if more than two dose reductions are required.
- IMP must be permanently discontinued in case of a dose delay of more than 14 days due to toxicity possibly related to GEN1029 unless otherwise approved by the sponsor medical monitor.

Adverse events that do not fulfill the DLT criteria should be handled as following (*specific rules apply for elevated liver parameters. Please see Section* 7.2.2.1):

• The investigators are encouraged to contact sponsor in case of any safety concern that need thorough discussion and evaluation.

